#### Principal Investigator: [name] ([name]), [name]

#### Introduction

The iliotibial band (ITB) is a thick fibrous fascial tissue that lies between the iliac crest and the anterolateral region of the thigh. Proximally it represents the insertional tendon of two muscles placed in parallel: the tensor fascia latae (TFL) anteriorly; the superficial gluteus maximus posteriorly (Standring 2004).

Several researches link an incorrect ITB tension to some pathologies, such as: iliotibial band syndrome (Foch et al. 2020; Friede et al. 2020; Friede et al. 2022); patellofemoral chondropathy (Park et al. 2016); cruciate ligament injury (Cibulka and Bennett 2018; Liebensteiner et al. 2020; Xu et al. 2021; Runer et al. 2022); low back pain and sciatica (Arab et al. 2010).

The mechanical importance of ITB is highlighted by the prevalence with which the latter is involved, particularly in runners, in fact 5 to 14% of all running-related injuries involve ITB (Van Der Worp et al. 2012).

One would expect that for a structure so susceptible to injuries and with a close functional connection with various pathologies, there would be a reliable evaluation and diagnosis test, but unfortunately this is not the case.

The manual tests proposed in the literature to evaluate the tension of the ITB are the classic (Ober 1936) and the modified Ober test (Kendall 1994, page 57). In the literature there are some studies (Melchione and Sullivan 1993) that have validated the repeatability of the Ober test, both the classic and the modified one, but none has ever confirmed its validity. Both of these tests indirectly evaluate the tension of the ITB through the degree of adduction of the femur.

The work of Willett et al. (2016), carried out with cadaveric findings, reports that the structures involved during passive adduction of the femur are different and the main ones that limit the excursion are the gluteus medius, the minimus and the capsulo-ligamentous structure. The question that arises spontaneously, taking into consideration the results of this last study, is: how else can we evaluate the tension of the ITB in order to be able to correlate it to the pathology reported in the literature? From the lack of validation of the manual tests described in the literature and commonly used in clinical practice, the need emerges for a new test that makes the assessment of the ITB tension more reliable.

The direct manual evaluation of the tension of the ITB certainly turns out to be more specific (valid/accurate) but arises doubts as to how reproducible it can be.

The proposed study will try to investigate the reliability of direct palpation of the ITB, investigating the reproducibility of the intra- and inter-examiner evaluation performed on the same day (intra-day) and validate the result of the palpatory examination with an instrument that measures tissue tension. It will also be evaluated whether concordance can be improved by appropriate training.

#### **Material and Methods**

The recruitment phase involves the enrollment of asymptomatic young/adult subjects for pathologies of the lower limbs which, in the opinion of the subject himself or the examiner, make detection difficult.

The number of subjects to be recruited was chosen following the indications provided by the International Academy of Manual/ Musculoskeletal Medicine (Patijn 2019).

The enrollment will take place in three distinct phases, each for every phase of the study which involves the evaluation of subjects. In the first (baseline sampling) 40 subjects will be recruited, in the second (verification

sampling) 20 and in the third (final sampling) 40. Consent will be requested each time. Since it is possible that the same subject is recruited several times (since it is not relevant for the purposes of the assessment whether the subjects are different or the same - Patijn 2019) the total number of subjects involved may vary between a minimum of 40 and a maximum of 100.

MyotonPRO (MyotonPRO-Estonia) is a digital palpation device for the non-invasive measurement of the condition of muscle tone, myofascial stiffness and elasticity with good validity and repeatability of the results both in healthy subjects (Chen et al. 2019) and in pathological subjects (Garcia-Bernal et al. 2021). The device features a mechanical actuator, which delivers a percussive pulse to the myofascial structure and records the response. Subsequently, filtering and digital processing are used to process the data and calculate numerical parameters of muscle tone, biomechanical and viscoelastic properties.

#### **Inclusion criterion**

- subjects aged between 18 and 40 years.

#### **Exclusion criteria**

- Clinically evident pain symptoms which, in the opinion of the subject or the examiner, may prevent the execution of the test (for example hip pain while maintaining the sampling position);

- obvious excess weight (BMI greater than 28 kg/m2) which could undermine the manual and instrumental result obtained.

#### **Project phases**

The project includes 6 phases:

I phase - agreement in principle on the sampling method;

II phase - recruitment;

III phase - first sampling;

- IV phase training on perception and concordance;
- V phase second sampling to verify the progression of the agreement;
- VI phase third manual sampling and evaluation with Myoton.

#### **Description of the phases**

I phase - The two examiners together with the principal investigator perform 2 hours of training to standardize the sampling method (localization of the point to be evaluated of the ITB and intensity of pressure of the fingertips to be used) and discussion on the tension gradation detected on the ITB with some volunteers.

II phase - The recruitment will be carried out through the search for volunteers among the students of the OSCE-Bologna school of osteopathy, through announcement in the classroom and publication of the

recruitment in the FB social group of the school (OSCE planet) and WhatsApp groups of students organized by year.

III phase - First sampling of manual evaluation only, using a sample of 40 subjects (both limbs), as proposed in the literature (Patijn 2019).

The operators identify if there is an equal or different stiffness between the right and left ITB.

There will be a double evaluation for each sampling session: 1) if there is a uniformity of the tension between the two sides, or if there is a prevalence on one side; 2) quantification of the difference, if present, with a graduation in 3 levels.

In the first sampling, the examiner will indicate with + 1 a greater tension on the right side; - 1 on the left side; 0 if there are no significant differences.

The second sampling consists in identifying, when present, the graduation of the tension difference between the two sides, arlTBrarily divided into 3 levels. The examiner will then report:

+ 3 to indicate more tension on the right with a large difference from the left;

+ 2 to indicate greater tension on the right with a medium difference compared to the left;

+ 1 to indicate more tension on the right with a slight difference from the left;

0 to indicate an insignificant prevalence of tension on one side with respect to the other;

- 3 to indicate greater tension on the left with a large difference compared to the right;

- 2 to indicate greater tension on the left with an average difference with respect to the right;

- 1 to indicate more tension on the left with a slight difference compared to the right.

IV phase - The manual examiners carry out a period of training on perception and agreement, lasting about 20 hours. This training is done using tools (gold standard) made specifically to change the state of density and tension of elastic structures and ropes that simulate the ITB, connected to dynamometers to quantify the state of tension. In vivo evaluation, between operators, are used to verify the exact point of where to take the tension sample and compare the tension data obtained for the construction of the agreement.

V phase - The second sampling to verify the progression of manual agreement, as proposed in the literature (Patijn 2019), is carried out by evaluating the tension of the ITBs, with the same method as the first sampling with volunteers, but in a reduced sample (about 20 subjects). If from the statistical processing of the results of this trial evaluation a good improvement in the agreement is highlighted, compared to the previous sampling (baseline) weighted Cohen's K value greater than or equal to 0.60, the program moves on to the VI phase; otherwise, there will be additional training.

VI phase - The definitive manual sampling consists in repeating, using the same modality of the first evaluation (baseline), with different or identical subjects of the first sampling. The number of subjects will always be 40 evaluated by both examiners and each examiner will evaluate the same subject twice about 20-60 minutes apart. The same subjects will be tested, after the manual evaluation, with the Myoton using the

modality previously described. The results of the Myoton are automatically stored in the preset instrument with the subject ID and downloadable to the computer in an Excel worksheet.

All the data obtained is collected and processed by the examiner who does not participate directly in the data collection using an Excel spreadsheet and/or the R program.

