#### Settings

The samplings will be made in a room with two beds arranged about 3 meters apart and two desks. A screen, placed on both beds, will cover the examined subject from the pelvis upwards. The same subject is evaluated, on the same day, by both examiners twice, approximately 20-60 min apart.

Two subjects at a time are made to enter the room where the two manual examiners are present; a third examiner will use the Myoton.

When the 2 subjects enter the room and lie down in a supine position on the bed, with both limbs uncovered, the operator keeps their feet together, with a Velcro strap, to symmetrize the major axis of the feet and indirectly rotation of the hip.

During this preparation of the subjects to test, the manual examiners are turned away so as not to identify the test subjects. Once the positioning is complete, the examiners turn around and have 15 seconds to evaluate the assigned subject (see figures - examiner A always evaluates the subject on the right bed first while examiner B the one on the left); once the subject has been evaluated and the subject's identification code has been reported on a piece of paper with the result of the evaluation which is placed in a container, they go on to evaluate the subject lying on the opposite bed and repeat the same procedure for recording and storing the data detected.

Once the manual evaluation test has been carried out by both examiners, the subjects, before getting off the bed, are evaluated by the examiner who uses the Myoton, following the instructions recommended by the manufacturer. The examiner traces an X with a pen on the evaluation point, about 5 cm proximally from the joint line and 1 cm from the anterior edge of the ITB, and then carries out the evaluation which automatically takes place through 3 impulses. The result is automatically stored in the preset instrument with the subject ID.

The parameters measured and stored are:

F – Natural oscillation frequency [Hz], which characterizes the tone or tension S – Dynamic stiffness [N/m]

D – Logarithmic decrease of the natural oscillation, which characterizes the elasticity R – Mechanical stress relaxation time (ms)

C – Ratio of strain and relaxation time, which characterizes the "Creep" (Deborah number).

At the end of all the evaluations, the examiner who manages the Myoton downloads the detected data onto the computer which is automatically stored on an Excel sheet.

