#### Outcomes

The study foresees the following outcome:

verify the increase in the agreement after the specific training (comparison between the agreement of the first sampling and that of the final sampling).

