#### **Expected total duration**

The total duration of the study including all the phases reported is approximately 2 months.

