#### **Statistical processing**

Processing of descriptive data of the subjects (age, weight and height).

Evaluation of intra and inter examiner agreement by means of weighted Cohen's K with use of sampling evaluation divided into 3 intervals (+1, 0, -1) and 7 intervals (+3, +2, +1, 0, -1, -2, -3).

The Myoton data are processed by subtracting the average data of the three measurements (automatically carried out by the instrument) of the right limb from that of the left. The data obtained is categorized into 3 levels to be compared, again using weighted Cohen's K, with the data from the manual evaluation.

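### Does the plan need to name which weighted kappa must reach 0.60 before the final sampling?

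*Combined protocol and SAP*

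**What the plan says.** Under Description of the phases, V phase repeats the manual ratings in about 20 subjects after roughly 20 hours of training. The study proceeds if "a good improvement in the agreement is highlighted, compared to the previous sampling (baseline) weighted Cohen's K value greater than or equal to 0.60"; on that result "the program moves on to the VI phase; otherwise, there will be additional training".

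The Statistical processing section evaluates intra- and inter-examiner agreement "by means of weighted Cohen's K with use of sampling evaluation divided into 3 intervals" and also into 7. It gives no weighting scheme. Under Settings, "The same subject is evaluated, on the same day, by both examiners twice, approximately 20-60 min apart", so every sampling yields two rounds from each of two examiners.

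The only listed outcome is to "verify the increase in the agreement after the specific training", comparing the first sampling with the final one. VI phase also serves the aim in the Introduction to "validate the result of the palpatory examination with an instrument that measures tissue tension". Material and Methods allows for one verification sampling of 20 subjects, and the expected duration is about 2 months.

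**The concern.** A go/no-go rule should give one answer for one set of data, and this one does not. With two scales, two intra-examiner comparisons and two inter-examiner comparisons (one per round), there are 2 × (2 + 2) = 8 candidate kappas, or 16 if linear and quadratic weights both count. No section selects one or says that all must pass.

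Two further points in the same sentence are loose. No connecting word says whether 0.60 defines the improvement or is a second condition. After a failure the text promises more training but does not say how often the check is repeated.

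If the bar moved with the choice of kappa, the examiners might enter VI phase with weaker agreement than intended, or train well beyond the stated hours. The comparison with the instrument and the reading of the training effect would then rest on a checkpoint without a fixed meaning.

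**Working it through.** **Inputs from the plan.** Threshold 0.60; about 20 subjects in V phase; 40 at baseline and 40 in VI phase; 3-level and 7-level scales; two examiners, two rounds. The threshold is a chosen value with no derivation, so there is no figure to reproduce.

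**Can the verdict flip on the same ratings?** Weighted kappa is 1 − (mean observed distance)/(mean distance expected from the margins), with distance |a − b| for linear weights. Take 20 invented subjects, with the 3-level score as the sign of the 7-level score.

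Examiner A: −3, −2, −2, −1, −1, −1, 0, 0, 0, 0, 0, 0, 1, 1, 1, 2, 2, 2, 3, 3.

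*Example 1.* Examiner B: −1, −2, −1, −2, 0, −1, 0, 0, 1, 0, −1, 0, 2, 0, 2, 1, 3, 3, 2, 1.
- 3 levels: observed 4/20 = 0.20; both margins 6/6/8, expected 360/400 = 0.90; kappa = 1 − 0.20/0.90 = 0.778 (pass).
- 7 levels: observed 16/20 = 0.80; expected 690/400 = 1.725; kappa = 1 − 0.80/1.725 = 0.536 (fail).

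*Example 2.* Examiner B: −2, −2, 0, 0, −1, 0, −1, 0, 1, 0, 0, 1, 0, 1, 0, 2, 1, 2, 3, 2.
- 3 levels: observed 8/20 = 0.40; expected 344/400 = 0.86; kappa = 1 − 0.40/0.86 = 0.535 (fail).
- 7 levels: observed 12/20 = 0.60; expected 648/400 = 1.62; kappa = 1 − 0.60/1.62 = 0.630 (pass).

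So the verdict can flip, and neither scale is always the stricter. With quadratic weights both examples pass on both scales (0.855 and 0.788; 0.683 and 0.834).

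**How often?** This needs category shares, which the documents do not give. Assumptions: a latent normal subject value plus independent examiner error, no examiner bias, inter-examiner agreement in the first round, n = 20, 40,000 simulated samples per setting (Monte Carlo error about √(0.5 × 0.5/40,000) = 0.25 percentage points). Left/equal/right shares are 35/30/35%, with the range taken over 25/50/25, 15/70/15 and 45/10/45 as well.

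| Kappa used, true 3-level linear kappa 0.5 | Its true value at 35/30/35 | Chance of reaching 0.60 (range over shares) |
|---|---|---|
| 3-level linear | 0.500 | 24-29% |
| 3-level quadratic | 0.603 | 37-51% |
| 7-level linear | 0.475 | 12-20% |
| 7-level quadratic | 0.683 | 53-71% |

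At least one of the four passes in 60-74% of samples, and all four in 10-16%. At a true 3-level linear value of 0.8, all four pass in 86-94%. A repeat run with separate code at 35/30/35 gave 23.5, 49.9, 11.9 and 71.2% for the four rows, in agreement with 24.0, 50.1, 12.2 and 71.2%.

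The check still discriminates once one kappa is fixed. For 3-level linear at 35/30/35, the chance of passing at true values 0.4, 0.5, 0.6, 0.7 and 0.8 is 9.5, 24, 49, 77 and 95%. If the check is repeated with no gain in between, two failures in a row have probability (1 − 0.240)² = 0.58 at true 0.5 and (1 − 0.770)² = 0.05 at true 0.7. An unspecified number of repeats therefore matters mainly where agreement really is below the bar.

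**What does the choice feed into?** VI phase rates 40 subjects afresh. With independent rating error, a lucky or unlucky V phase contributes nothing to the VI-phase kappa. The listed outcome uses the first and final samplings, so V-phase data do not enter it. A lenient choice means less training before VI phase, and a strict choice means more. Either way the final sampling estimates the agreement that the examiners actually reached.

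**The case for a change.** The strongest case for acting is that the sentence is a decision rule, that scale or weights alone can reverse it, and that a few words before V phase would settle it at no cost. The gap itself stands: no section closes it. V phase cites a published reproducibility protocol, but what that source says about kappa cannot be seen from these documents and cannot be relied on either way.

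Several parts of the case are weaker than they look.
- Intra versus inter is less open than a count of 16 implies. The phases list describes the training as concerning concordance, IV phase compares evaluations between operators to build agreement, and V phase tracks its progression. That points to inter-examiner agreement.
- The 35/30/35 shares sit at the end of the range that favours the concern for most contrasts, so the ranges are the fair summary.
- The four kappas measure different things. A 7-level quadratic kappa whose true value is 0.683 is not wrongly passed at 0.60.
- Nothing in the text suggests that the kappa would be picked after the ratings are seen.
- The simple reading of the loose sentence is that 0.60 is the criterion, and that a failure leads to more training and another check.

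It remains true that the training delivered before VI phase could exceed the planned 20 hours or so, and that weaker examiner agreement would lower agreement with the instrument. VI phase measures examiner agreement in the same 40 subjects, so a reader sees both together.

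**Conclusion.** No change to the plan follows. The rule leaves scale and weights unnamed, and near the threshold this matters to the checkpoint: at a true 3-level linear kappa of 0.5, the chance of passing runs from 12-20% to 53-71% across the four inter-examiner versions. The effect ends at the checkpoint. It governs how much training precedes VI phase. It does not bias the final kappa or the first-versus-final comparison, and it largely disappears when agreement is clearly good. Any sensible inter-examiner weighted kappa, applied consistently, leaves the study's conclusion sound, so this is detail that the analysts can supply. The pass rates rest on assumed category shares, no examiner bias and independent rating error. The conclusion does not depend on the exact rates: it rests on the final ratings being new and on V-phase data not entering the listed outcome.

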# **Operators and Settings**

# Operators

Five operators will participate in the study:

- 1 operator, outside the sampling room, performs: registration by anonymizing the subject with an ID which is assigned to the subject by means of a piece of paper; distributes the information and collects informed consent to participate in the study; performs the post-collection processing (tabulation and statistics) of the collected data.

- 2 operators, inside the sampling room, carry out the manual sampling of the tension of the ITB;

- 1 operator, inside the sampling room, carries out the instrumental sampling (Myoton) of the tension of the ITB;

- 1 operator, inside the sampling room, who organizes the entry and exit of the subjects evaluated, giving the detection times.

#### Settings

The samplings will be made in a room with two beds arranged about 3 meters apart and two desks. A screen, placed on both beds, will cover the examined subject from the pelvis upwards. The same subject is evaluated, on the same day, by both examiners twice, approximately 20-60 min apart.

Two subjects at a time are made to enter the room where the two manual examiners are present; a third examiner will use the Myoton.

When the 2 subjects enter the room and lie down in a supine position on the bed, with both limbs uncovered, the operator keeps their feet together, with a Velcro strap, to symmetrize the major axis of the feet and indirectly rotation of the hip.

During this preparation of the subjects to test, the manual examiners are turned away so as not to identify the test subjects. Once the positioning is complete, the examiners turn around and have 15 seconds to evaluate the assigned subject (see figures - examiner A always evaluates the subject on the right bed first while examiner B the one on the left); once the subject has been evaluated and the subject's identification code has been reported on a piece of paper with the result of the evaluation which is placed in a container, they go on to evaluate the subject lying on the opposite bed and repeat the same procedure for recording and storing the data detected.

Once the manual evaluation test has been carried out by both examiners, the subjects, before getting off the bed, are evaluated by the examiner who uses the Myoton, following the instructions recommended by the manufacturer. The examiner traces an X with a pen on the evaluation point, about 5 cm proximally from the joint line and 1 cm from the anterior edge of the ITB, and then carries out the evaluation which automatically takes place through 3 impulses. The result is automatically stored in the preset instrument with the subject ID.

The parameters measured and stored are:

F – Natural oscillation frequency [Hz], which characterizes the tone or tension S – Dynamic stiffness [N/m]

D – Logarithmic decrease of the natural oscillation, which characterizes the elasticity R – Mechanical stress relaxation time (ms)

C – Ratio of strain and relaxation time, which characterizes the "Creep" (Deborah number).

At the end of all the evaluations, the examiner who manages the Myoton downloads the detected data onto the computer which is automatically stored on an Excel sheet.

After the manual and instrumental detection, the subjects leave the sampling room and remain in the area for when they will be recalled for the second evaluation.

At a variable distance of 20-60 minutes from the first survey, the tested subjects are recalled, this time only for the manual re-evaluation, in the same way as in the previous evaluation, using a different sequence and identification code from the one used in the first examination.

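### Both legs are bare at the 20-60 minute re-test and recognition is never recorded, so intra-examiner kappa can be biased upward by an unknown amount

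*Combined protocol and SAP*

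**What the plan says.** All of this is in the Settings section of the combined protocol and SAP unless stated otherwise.

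- **Aim of the masking.** During positioning, "the manual examiners are turned away so as not to identify the test subjects".
- **Extent of the masking.** "A screen, placed on both beds, will cover the examined subject from the pelvis upwards". Below that level nothing is hidden: subjects "lie down in a supine position on the bed, with both limbs uncovered".
- **Viewing.** Once positioning is complete, "the examiners turn around and have 15 seconds to evaluate the assigned subject".
- **Re-test.** "The same subject is evaluated, on the same day, by both examiners twice, approximately 20-60 min apart". The recall is "this time only for the manual re-evaluation, in the same way as in the previous evaluation", so the legs are exposed again. This follows from the cross-reference and is not stated separately.
- **Safeguards at re-test.** The recall is made "using a different sequence and identification code from the one used in the first examination".
- **Pen mark.** When the Myoton is used, its operator draws an X on the evaluation point after the first manual rating and before the re-test. No removal is described.
- **Analysis.** Statistical processing plans weighted Cohen's kappa for intra- and inter-examiner agreement, on 3 and on 7 categories. Outcomes lists one item, the increase in agreement from the first to the final sampling.

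The documents do not mention covering leg features, asking examiners whether they recognised a subject, or checking whether the masking worked.

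**The concern.** A test-retest kappa measures reproducibility only if the second rating is made without knowledge of the first. The plan accepts this, since it takes several steps to conceal identity. Those steps remove the face, the upper body, the code and the order as cues. They leave in view the region the examiner must look at and handle, where scars, tattoos, hair and build can distinguish one person from another. The gap between ratings can be as short as 20 minutes, and what has to be remembered is a single signed value on a 3- or 7-level scale.

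A remembered rating that is repeated enters the table as perfect agreement, so any such bias in intra-examiner kappa is upward. The Introduction names intra-examiner reproducibility as an aim of the study. As the plan stands, a reader of the result could not tell how much of the agreement came from palpation and how much from memory.

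**Working it through.** The documents give no recognition rate, no expected kappa and no power calculation, so there is no planned figure to reproduce. What follows is an illustration.

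**Inputs from the documents:** weighted kappa as the statistic (Statistical processing); 40 subjects at the first and final samplings and about 20 at the second; a kappa threshold of 0.60 before the final phase (Description of the phases, V phase).

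**Assumed inputs:** the recognised share r; the true intra-examiner kappa k; recognition unrelated to the rating; the same distribution of ratings in both rounds.

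**Step 1, formula.** Weighted kappa is 1 − D_o/D_e, the observed over the chance-expected weighted disagreement. If a share r of pairs is forced to agree, D_o becomes (1 − r)D_o and D_e is unchanged. Hence

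k′ = 1 − (1 − r)(1 − k) = k + r(1 − k).

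**Step 2, numbers.**

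| True k | r = 10% | r = 20% | r = 25% | r = 50% | r needed for 0.60 |
|---|---|---|---|---|---|
| 0.40 | 0.46 | 0.52 | 0.55 | 0.70 | (0.60 − 0.40)/0.60 = 33% |
| 0.50 | 0.55 | 0.60 | 0.625 | 0.75 | (0.60 − 0.50)/0.50 = 20% |

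For example, 0.50 + 0.20 × 0.50 = 0.60. At r = 0, k′ = k.

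**Step 3, check by simulation.** A 3-category rating with linear weights and true kappa 0.50 gave 0.553, 0.627 and 0.752 at r = 10%, 25% and 50%, in line with the formula. Quadratic weights followed the same rule: 0.609 at r = 0 became 0.650, 0.707 and 0.805. The plan does not state its weights.

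**Step 4, chance of observing at least 0.60** when the true linear-weighted kappa is 0.50 (4,000 simulated samples per cell):

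| n | r = 0 | r = 10% | r = 25% | r = 50% |
|---|---|---|---|---|
| 40 | 17% | 30% | 61% | 95% |
| 20 | 23% | 35% | 56% | 88% |

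**Step 5, effect on the before-after comparison.** With the same r at both samplings,

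k2′ − k1′ = (1 − r)(k2 − k1).

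A true rise from 0.40 to 0.60 with r = 20% is seen as 0.52 to 0.68, a gain of 0.16 instead of 0.20. Both levels are too high, but the gain is too small. If r differed between samplings, this simple shrinkage would not apply.

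**The case against.** The strongest reply is that nothing in the documents shows recognition or recall taking place. Inflation needs two events. The examiner must recognise a pair of legs after a rating of at most 15 seconds, and must also recall that subject's score among up to 40 others. Subjects return in a new order under a new code. This stands: the documents support a risk of unknown size, not a finding of bias.

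A reader might infer three stronger things, none of which the documents support.

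- *That recognition could carry the study past its own 0.60 threshold.* The V phase text does not say whether that threshold applies to intra- or inter-examiner kappa. If it is inter-examiner, the comparison is irrelevant, so 0.60 serves here only as a reference value.
- *That all the agreement results are inflated.* Within a round, inter-examiner agreement involves no earlier rating of one's own to repeat, so it is not directly affected.
- *That the apparent benefit of training is exaggerated.* With equal r at both samplings, the intra-examiner gain is understated (Step 5).

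There is also a fair objection to full draping with an opening only at the palpation site. Locating the point is part of what the examiners are trained to do (I and IV phases). Preselecting it would remove a real source of disagreement and could itself raise kappa. That objection also stands, and the fix allows for it.

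The pen X would be on every subject measured with the Myoton, so it does not identify anyone by itself. It does show the re-testing examiner where the instrument was applied, a cue that was absent at the first rating.

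None of this closes the gap. The plan's masking stops short of its stated aim, and the data it collects would not reveal whether that mattered.

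**Conclusion.** The point holds as a minor design weakness. The masking leaves visible leg features exposed at both ratings, and recognition is not recorded. If it occurs and the first rating is repeated, intra-examiner weighted kappa is biased upward by about r × (1 − k), which is 0.05 at r = 10% and 0.10 at r = 20% from a true value of 0.50. These sizes rest on assumed values of r and k, on similar rating distributions in the two rounds, and on recognition being unrelated to the rating. The true r may be zero. The effect is confined to intra-examiner kappa, and for the before-after comparison an equal r works against the study, not in its favour.

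**What to change.** 1. Add a subject-recognised yes/no tick to every second-round slip, completed by each examiner after the rating is written. Do this at all three samplings; it cannot be reliably reconstructed later.
2. State in Statistical processing that intra-examiner weighted kappa will be reported, at each sampling, for all subjects and excluding those the examiner recognised.
3. Where practical, cover the parts of the legs not needed for landmarking. Leave the knee and distal thigh visible so that examiners still find the point themselves. Keep the new code and new order.
4. In the final sampling, remove the Myoton pen X before the re-test.

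**Cost.** A few seconds of set-up per pair of subjects and one extra kappa per examiner. The sensitivity analysis has a slightly smaller sample: at r = 20%, 40 × 0.80 = 32 subjects would remain at the first or final sampling. The second kappa is therefore less precise and should be read beside the main one, not in place of it. If covering the legs proves awkward, items 1 and 2 alone turn an unknown bias into one that can be examined.
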